Recombinant human chorionic gonadotropin (r-hCG)(Ovidrel® Prefilled Syringe, Serono) will be purchased from Serono, Inc., Rockland, MA or Switzerland. Participants will receive a subcutaneous injection of 250 microgram-recombinant hCG three times a week (Monday, Wednesday and Friday) for 12 weeks. The first dose of study drug will be administered by a registered nurse. At that time, she will instruct each participant in the self-administration of the study drug in a skin fold of the upper abdominal region. Participants will return to receive doses 2 and 3, where they will be observed by the registered nurse in the self-administration of the drug for mastering of the skill and to answer any additional questions. The remainder of the drug doses will be self-administered by the participants or a partner trained in the procedure in their homes. All participants will be seen by a study physician once a month during the treatment phase for a history and physical exam and blood collection.

Protocol tissue collection

Normal breast tissue specimens will be collected by CNB at the beginning of treatment (0 day), at the end of treatment (90 days) and at six months post-treatment (270 days - 36 weeks). CNB specimens will be primarily utilized for analysis of genomic expression by cDNA microarray, RNA sequencing and epigenomic studies. In addition, a series of surrogate intermediate markers such as cytomorphologic evaluation and cell proliferation index will be analyzed. The primary objective is to compare the gene expression, and epigenomic profiles of sampled breast epithelial cells across the three time points (Fig. 1), before and after treatment, and identify differentially expressed or silenced genes (as determined by ≥ 2 fold change). Gene expression measurements will be obtained at baseline (time 0), after treatment with hCG at 90 days (time 1), and at 270 days from baseline (time 2). We are interested in comparing the expression profiles between all pairs of time points as well as across time. The comparison of profiles before and after treatment with either hCG, both at 90 and 270 days, are of particular interest (Figure 1).

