Each breast sample consists of four core biopsies. One core will be used for histopathological analysis and the other three for genomic analysis. All breast core biopsies must be obtained by a qualified physician and specimens are obtained after an authorization for use and disclosure of protected health information for research has been approved by the Institutional Review Board (IRB).

From the four core biopsies collected, the first one is preserved in 70% ethanol for histopathological evaluation; and the other 3 are preserved in an RNA-preserving fluid (RNAlater®, Ambion) for genomic analysis.

For histopathological analysis the first core is expelled from the needle into a pre-labeled 15 mL tube containing 10 mL of 70% ethanol. The needle is washed in isotonic sodium chloride solution before next use. The specimen is identified with name, personal ID, date, core number and stored for up to 4 weeks at 4°C in the original collection tube until ready for shipment by express mail in wet ice.

For RNA preservation the second, third and fourth breast core biopsies are immersed in 2.0mL of RNAlater® (Ambion cat# AM7020), in an Eppendorf tube that is identified specifying the name, ID, date, and solution lot number. The tubes containing the biopsies and RNAlater® should be first incubated overnight at 4°C to allow thorough penetration of the solution into the tissue, then transfer to –20°C, where they should be kept until shipment. The shipment can be by express mail in wet ice (4°C).

Participant selection

Inclusion criteria

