All the tubes containing CNB samples collected as described need to be kept at 4°C before shipping. As an additional measure each sample tube should be wrapped with Parafilm to prevent possible leakage during shipment. The samples have to be shipped by overnight express mail to the Breast Cancer Research Laboratory at the Fox Chase Cancer Center with frozen ice packs in the Styrofoam box. The samples need to be packed tightly so they do not move during shipping. The shipments should be sent Monday through Thursday to ensure the samples are collected accordingly and not to ship on *Fridays to ensure that the samples do not sit for an extended period of time.*

Special Studies

The following special correlative studies will be performed:

- #1, Histopathological evaluation of epithelial cell normality;
- #2, evaluation of cell proliferation by Ki67 immunohistochemistry;
- #3, serum analysis for hormone level and biomarker determinations;
- # 4, genomic analysis of breast epithelial cells from CNB.

Genomic DNA and total RNA will be extracted using ALLPrep DNA/RNA Mini Kit (QIAGEN) according to manufacture instructions.

Special Correlative study #1 - Cell Morphology and Proliferation:

Histopathological analysis - Outcome measures: A minimum of two slides will be made one for histology and another one for Ki-67.

Special Correlative study #2 - Cell proliferation - Ki67 index:

Total epithelial cells will be delineated with Mayer's hematoxylin counter stain and proliferating cells with a MIB-1 (DAKO M7240) antibody for Ki-67.

Special Correlative study #3 - Serum analysis for hormone level and biomarker determination:

At the time of each CNB, whole blood will be collected by venipuncture and stored in the FCCC Breast Cancer Research Laboratory at -80°C for batch determination of hormonal levels and aliquots will be stored for future studies. All serum assays for estradiol, progesterone and human chorionic gonadotropin will be conducted at the Breast Cancer Research Laboratory of the FCCC.

Special Correlative study #4 - Gene expression analysis.

Affymetrix U133plus2.0 microarrays will be used in this follow-up gene expression study involving 25 women each in the hCG treatment arm. Gene expression measurements will be obtained at baseline (before treatment) and at 3 months and 9 months after the respective treatment. We will identify genes that are

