significantly up or down regulated at 3 months following treatment. In addition, we will compare the post- and pre-treatment differences and identify genes showing significantly altered expression. We will repeat the above analyses using the post-treatment expression at 9 months.

Analysis of biomarker data.

In addition to microarray data, we will obtain expression levels of Ki67, ER, PR, estradiol, progesterone and hCG using serum assays at baseline (before treatment) and at 3 months and 9 months after treatment. We will identify markers that are significantly up or down regulated at 3 months following treatment. In addition, we will compare the post- and pre-treatment differences and identify markers showing significantly altered expression. We will repeat the above analyses using the post-treatment expression at 9 months.

Statistical Considerations.

The primary efficacy analyses for the phase I/II study will concern baseline to 3-month follow-up changes in gene expression profiles measured by microarray methods as follows. For each woman i at biopsy time point j (0 =pre-treatment, 1 =3 month follow-up) we will compute the Mahalanobis distance between RMA normalized expression microarray data derived from the biopsy and the prototypic gene profile. We will denote this distance as $D(i,j)$. If $D(i,1) < D(i,0)$ we will declare woman i a “success”. This would indicate the post-treatment profile (genomic signature) is closer than the pre-treatment profile to the prototypic gene profile. At the conclusion of the study we will sum the number of successes for each arm. Whichever arm has a higher proportion of successes is declared the “preventive choice”. With complete pre-treatment and post-treatment expression microarray data on 25 women we will correctly identify the changes in terms of “success” with at least 85% probability. Assuming a drop-out rate of 20%, we would need to enroll a total of 25 participants per arm.

In secondary analyses we will use an exact one-sided, one-sample test ($\alpha=0.05$) to assess the null hypothesis of no drug induced change in $D(i,j)$ (i.e., a null hypothesis that the probability of “success” is 0.5.). With data from 18 women we will have at least 80% power to detect the alternative hypothesis that the true probability of “success” is 0.80. We will also characterize the change in distance (i.e., $\Delta D(i)=D(i,1)-D(i,0)$) using standard methods (e.g., mean, median, standard deviations, etc.).

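### Tubes carry the participant's name and collection date and no masked reading is stated, so readers of Ki67 and histology can learn the time point in an uncontrolled before/after comparison

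*Protocol*

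**What the plan says.** Under the Protocol heading on tissue collection, each breast sample consists of four cores. The first goes to histopathology, and its tube is labelled as follows: "The specimen is identified with name, personal ID, date, core number". The other three go to genomic work, each "in an Eppendorf tube that is identified specifying the name, ID, date, and solution lot number". The histology core may be "stored for up to 4 weeks at 4°C in the original collection tube" before it is shipped to the research laboratory. Biopsies are taken at day 0, at day 90 and six months after treatment.

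The Special Studies section lists histopathological evaluation and "evaluation of cell proliferation by Ki67 immunohistochemistry" among the correlative studies. On slides it says: "A minimum of two slides will be made one for histology and another one for Ki-67". On the Ki67 method it says: "Total epithelial cells will be delineated with Mayer's hematoxylin counter stain and proliferating cells with a MIB-1 (DAKO M7240) antibody for Ki-67". It does not say who reads the slides, what label they carry, or in what order they are read.

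The section on analysis of biomarker data includes Ki67 among the markers for which "we will compare the post- and pre-treatment differences and identify markers showing significantly altered expression". The tissue collection section describes cytomorphology and the proliferation index as surrogate intermediate markers, analysed in addition to the genomic profiles.

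The opening summary has all 25 women receive the drug, and the Dutch summary calls the study open. The statistical section speaks of arms but defines no control group. The opening summary also reports a marked fall in Ki67 staining in earlier breast cancer patients given hCG.

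**The concern.** Without a control group, the within-woman change is the only evidence that the drug moves Ki67 or cell morphology. Counting stained epithelial cells and judging whether epithelium is normal both involve a reader's judgement. The protocol itself gives the reader a direction to expect. If the reader can see or work out the time point, expectation can shift the average reading downwards after treatment, and nothing in the design separates that shift from a drug effect.

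The label is written at the clinical site on the day of biopsy, and this document fixes it. It is not a detail that an analysis plan could repair after the specimens have been labelled and read.

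**Working it through.** **The plan's nearest figure.** The point disputes no number. The closest is the power statement under Statistical Considerations: 18 women, exact one-sided test at 0.05, null success probability 0.5, alternative 0.80.
- With X ~ Binomial(18, 0.5), P(X ≥ 12) = 0.119 and P(X ≥ 13) = 0.0481, so the cut-off is 13.
- With X ~ Binomial(18, 0.80), P(X ≥ 13) = 0.867, which agrees with the stated power of at least 80%.
- This test concerns the microarray distance, and nothing below changes it.

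**Can the time point be learned?**
- By label: name plus date orders one woman's tubes in time.
- By arrival: histology cores are held at most 4 × 7 = 28 days before shipment, and the first two biopsies are 90 days apart. Since 28 < 90, a woman's baseline and end-of-treatment cores cannot share a shipment. Reading specimens as they arrive would reveal the time point even without the label.

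**Does anything offset this?** The protocol describes no specimen coding, slide relabelling, masked reader or random reading order. Its only mention of blinding concerns a cited obesity study.

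**Illustration of size.** Only the first input comes from the protocol.
- Pairs: 25 women and 20% drop-out give n = 25 × (1 − 0.20) = 20.
- Test (assumed): two-sided 5% paired t-test, 19 degrees of freedom, critical value 2.093.
- True change: none. The mean reading shift is δ, in SDs of the paired difference (assumed).
- False-positive rate = P(|T| > 2.093), where T is noncentral t with 19 df and noncentrality δ√20.

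| δ (assumed) | δ√20 | False-positive rate |
|---|---|---|
| 0.1 | 0.447 | 0.071 |
| 0.25 | 1.118 | 0.186 |
| 0.5 | 2.236 | 0.565 |

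With 18 pairs the rates are 0.069, 0.170 and 0.516, so the picture does not depend on the exact number.

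**A second illustration.** Suppose slide readings were scored only as improved or not, with 18 women and the cut-off of 13. If expectation moved the chance of an improved reading from 0.50 to 0.55, 0.60 or 0.65, the false-positive rate would rise from 0.048 to 0.108, 0.209 or 0.355. These shifts are also assumed.

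**The case against.** The strongest reply is that the label rule covers collection tubes only. Slides are cut later, and the laboratory could code them and mask the reader without breaching any sentence of the protocol. Slide labels and reading order are often set in a laboratory manual or analysis plan, and neither is at hand. This stands in part. A reader might infer that the slide readers do know the time point, but the text does not show that. It supports only the statement that they can learn it and that no safeguard is written down.

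Three further inferences are tempting and are not supported.
- **That the primary result is compromised.** The primary analysis is a Mahalanobis distance from RMA-normalised array data, which no reader scores.
- **That decisions to drop poor arrays are biased in the same way.** The protocol describes no such exclusion step.
- **That every pair is pushed the same way.** A shift in the mean reading need not move each pair.

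It is also fair to say that the error rates are hypothetical. The protocol names no test for Ki67 and gives no size of reader bias, and it does not show that histological normality is a continuous measure, so the t-test illustration does not cover it.

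What remains is that a stated labelling rule discloses name and date, a reader-dependent marker is compared before and after treatment without controls, and the expected direction is in print.

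**Conclusion.** The concern holds for the correlative slide markers, Ki67 and histology. Tubes labelled with name and date, with no coding or masked reading stated, leave the before/after comparison of these markers open to reader bias. The stated pre/post comparison names Ki67. Histology is exposed in the same way as a surrogate marker from the same cores, although its analysis is not spelled out.

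The size is unknown. Under the assumed test with 20 pairs, mean shifts of 0.1 to 0.5 SD would raise a nominal 5% error rate to between 7.1% and 56.5%, and the upper figure depends on the largest assumed shift. This is worth correcting because the correction is cheap. It is not a flaw in the primary efficacy analysis, and it changes no sample size.

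**What to change.** - Label specimens and slides with a study code that shows the reader neither name nor time point.
- Keep the key and the collection date in a log away from the reader, so that the 4-week storage limit can still be checked for each core.
- Have each woman's Ki67 and histology slides read together, in random order, by a reader masked to time point. Joint reading also removes the clue given by arrival order, which a code alone would not.
- State these steps in the protocol sections on tissue collection and special studies.

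The cost is a code list, a label change and some site logistics. Baseline slides must also be held until after the last biopsy, about 270 days by the protocol's day count. No extra reader, visit or procedure is needed.

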The preclinical interval between generation of susceptibility and appearance of the diseases offers opportunities for primary prevention and presumably has a period when genetic control is modifiable. Reversibility declines progressively when different premalignant or early malignant phenotypes appear. Early detection becomes now the priority and can be achieved through recognition of risk markers that reliably predict disease. Newer sophisticated imaging techniques detect the disease in phases where cure is expected. But these tools don't address the rapid mortal threat of breast cancer in the third world. This is now the prime concern for the next generations worldwide that probably are best served with affordable primary prevention. High priority must be given to lifestyle research on affordable reversion of (epi-) genomic alterations.

One event that restores effectively genomic alterations is an early full time pregnancy, that reduces breast cancer risk. High risk genomic signatures are converted to low risk signatures. The principal hormone responsible for this risk reduction is hCG. Consequently, treatment with hCG could have the same preventive capabilities compared to a full term pregnancy and could serve as a preventive treatment for high risk patients.

hCG is a safe and effective drug, commercialized under the name of Ovidrel. Earlier experience in treating women with breast cancer showed drastic reduction in Ki67 staining in cancer cells while no adverse reactions were noted. Similar experience is seen in infertility treatments where limited side effects are seen. The safety profile of this drug, together with the potential efficacy in reducing breast cancer risk, made the scientific community to believe that hCG treatment could be applied to healthy women at increased risk.

One of the best established risk factors is BRCA1 germ line mutation that confers a life time risk of up to 70%. In this proof-of-concept study, 25 patients will be selected for a 12 weeks treatment of Ovidrel. Before, immediately after and 1 year later the breast parenchyma will be examined by high-output molecular biology to find out if the "high-risk" genetic signature is effectively converted to "low-risk" signature in a similar way as early first full time pregnancy (FFTP) does.

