If this project succeeds in its goal to show change in genetic risk signatures, not only an effective preventive hormonal therapy is provided for the woman at increased risk but also an intermediary risk factor (before the disease becomes clinically evident) is characterized. An intermediary risk factor identifies women at increased risk prior to the disease but also serves as a monitor to guide preventive strategies.

Nederlandstalige samenvatting

Doelstelling en beschrijving van het studieprotocol

Dit is een klinische studie inzake een behandeling met studiegeneesmiddelen bij ca. 25 deelnemers, van wie zo'n 20 in België. Enkel gezonde vrouwen met een genetisch defect in BRCA1 gen zullen worden uitgenodigd om deel te nemen.

Het is een open studie dat het studiegeneesmiddel Ovidrel onderzoekt. Ovidrel zou de borstcellen beschermen tegen kankervorming doordat de kankerverwekkende eigenschap van het afwijkend gen BRCA1 gen door de veranderingen in het genetisch materiaal uitgeschakeld wordt.

Verloop van de studie

De studie neemt ongeveer 12 weken in beslag en omvat subcutane injecties van Ovidrel driemaal per week gedurende 12 weken. Maandelijks wordt de deelnemster gezien door de arts waarbij ook een bloedname gebeurt. Bovendien worden 3 lichte ingrepen uitgevoerd in de borst waarbij weefsel wordt weggenomen. Deze ingreep gebeurt ambulantly (op de raadpleging) op een zo comfortabele manier als mogelijk. Hierdoor wordt de ingreep vrijwel pijnloos. De ingreep is voor de behandeling, onmiddellijk na de behandeling (week 12) en in week 36 vanaf de start van de behandeling.

Intake consultatie

Tijdens een eerste consultatie zal de arts-onderzoeker samen met de deelnemster nagaan of deze in aanmerking komt voor de studie (inclusiecriteria) en of er geen situaties zijn waarin deelname niet mogelijk is (exclusiecriteria).

Inclusiecriteria:

- Asymptomatische vrouw vanaf 18 jaar
- BRCA1 positief
- Karnofsky 100%
- Geen borstkanker
- Participeert niet in andere studie(s)
- Neemt geen tamoxifen
- Geen voorafgaande kanker gehad (uitz. Niet-melanoma huidkanker)
- Normale ovaria op ultrasound
- Begrijpt informatie en onderschrijft schriftelijk "informed consent"
- Akkoord om de klinische studie aan te gaan
- Niet zwanger
- Akkoord voor mechanische contraceptie (abstinentie, barrièremiddelen, tubaligatuur)

Exclusiecriteria

- Geschiedenis van allergie tov r-hCG
- Hormonale medicatie
- IVF behandeling in het verleden
- Actuele ziekten
- Hartafwijkingen

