The study (Figure 1) is based on preclinical data that have demonstrated that hCG exerts a mammary cancer preventive effect, mediated by the induction of gland differentiation, which results in permanent changes in the genomic signature of this organ. This exploratory study will evaluate the genomic profile of breast epithelial cells obtained from Core Needle Biopsy (CNB) specimens performed in high risk women treated for 90 days with hCG.

Time line

Asymptomatic women of all racial and ethnic groups greater than 18 years old who are high risk for breast cancer (BRCA1 mutation); ECOG performance status 0 (Karnofski 100%); no clinical evidence of breast cancer; currently not participating in a chemoprevention trial for breast cancer or currently taking tamoxifen for chemoprevention; no history of prior cancer other than non-melanoma skin cancer; normal ovarian size report from pelvic ultrasound; ability to understand and willing to sign a written informed consent document; willing to self-administer or have the Ovidrel administered 3 X per week by a partner, (for 12 weeks, Subjects may not be pregnant because the effects of hCG on the developing human fetus are unknown. Subjects will be required to have a negative urine or serum pregnancy test within 72 hours of the 1st dose. Women of child-bearing potential must agree to use adequate contraception, including barrier method of birth control, abstinence or tubal ligation performed prior to study entry and for the duration of study participation. Should a woman become pregnant or suspect she is pregnant while participating in this study, she should inform her treating physician immediately.

Treatment plan

Women will receive three injections of 250 mcg hCG (Ovidrel) per week for a total of 12 weeks.

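### The primary efficacy rule compares arms, but the protocol describes one arm, so the rule cannot be applied and its 85% figure cannot be reproduced

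*Protocol*

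**What the plan says.** **Design.** The opening summary of the Protocol states: "In this proof-of-concept study, 25 patients will be selected for a 12 weeks treatment of Ovidrel". The Dutch-language summary calls it an open study of that one drug: "Het is een open studie dat het studiegeneesmiddel Ovidrel onderzoekt". The Treatment plan gives every woman the same regimen: "Women will receive three injections of 250 mcg hCG (Ovidrel) per week for a total of 12 weeks". No section describes a control group, a second treatment or an allocation procedure for this trial. The placebo comparison in the adverse-event section belongs to an earlier study in breast cancer patients.

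**Primary analysis.** Under Statistical Considerations, a woman is a success if her 3-month expression profile lies closer to the prototypic profile than her baseline profile does, that is, if D(i,1) < D(i,0). The rule continues: "At the conclusion of the study we will sum the number of successes for each arm". Then: "Whichever arm has a higher proportion of successes is declared the" preventive choice. The plan claims at least 85% probability of correct identification with complete data on 25 women. Allowing for 20% drop-out, it enrols 25 per arm.

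**Secondary analysis.** The next paragraph gives an exact one-sided one-sample test at alpha 0.05 of a success probability of 0.5. It claims at least 80% power with 18 women if the true probability is 0.80.

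**Other multi-arm wording.** Special Correlative study #4 speaks of a study "involving 25 women each in the hCG treatment arm". The exploratory paragraph of Statistical Considerations mentions a control group and more than one treatment.

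**The concern.** A rule that ranks arms needs at least two of them. Here it is the stated primary efficacy analysis, and the protocol provides one arm. The rule sets no minimum success proportion, so nothing in it says what result would count against hCG. The only operating characteristic attached to it, the 85%, comes without the assumptions needed to check it.

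The trial seeks proof of principle for a preventive treatment. At stake is whether its headline conclusion rests on a rule that can fail, with a known error rate, or on one that has to be reinterpreted once the data are in. The protocol already contains a suitable test of the same endpoint but ranks it below the unusable rule.

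**Working it through.** **1. Can the rule be applied?** The design sections give one arm, and the rule needs a higher proportion among arms. With one arm there is nothing to compare, so the rule is undefined. If the only arm is taken as the winner by default, P(select hCG) = 1 for any true success probability p, including p = 0.5 and below.

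**2. Can the 85% be reproduced?** Not from the protocol, because it gives no success rates. Under an assumed two-arm reading, the selection probability is P(X_A > X_B) + ½·P(X_A = X_B) for independent binomials with n per arm, ties split.

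| n per arm | Poorer arm | Better arm | Probability |
|---|---|---|---|
| 25 | 0.50 | 0.60 | 0.761 |
| 25 | 0.50 | 0.65 | 0.859 |
| 25 | 0.60 | 0.75 | 0.872 |
| 25 | 0.65 | 0.80 | 0.883 |
| 25 | 0.80 | 0.90 | 0.839 |
| 20 | 0.50 | 0.65 | 0.831 |

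With 0.50 assumed in the poorer arm, 85% needs a gap of about 0.145 at 25 per arm (0.163 if ties do not count) or 0.162 at 20 per arm (0.183). Many pairs of rates give about 85%, and the protocol names none.

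A single-arm reading is also possible. If correct identification means a majority of 25, then P(X ≥ 13) = 0.846 at p = 0.60. That comes close to 85%, but again needs a rate the protocol does not state.

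**3. Sample size behind the 85%.** 25 × (1 − 0.20) = 20 complete pairs, not 25. Having 25 complete pairs would need 25 / 0.80 = 31.25, so 32 enrolled.

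**4. What error would a simple majority carry?** At p = 0.5, P(X ≥ 13 of 25) = 0.50 and P(X ≥ 11 of 20) = 0.41. Reading the rule as a majority would not rescue it.

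**5. The secondary test.** P(X ≥ c) = Σ from x = c to n of C(n,x) pˣ(1−p)ⁿ⁻ˣ, where c is the smallest count with P(X ≥ c) ≤ 0.05 at p = 0.5. Power is taken at p = 0.80.

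- The plan's own case, n = 18: c = 13. Alpha = (8568 + 3060 + 816 + 153 + 18 + 1) / 2¹⁸ = 12616 / 262144 = 0.0481; power 0.867. The claim of at least 80% is confirmed.
- n = 20, the number expected after drop-out: c = 15. Alpha = 21700 / 1048576 = 0.0207; power 0.804. A cut-off of 14 would give alpha 0.058.
- n = 25, no drop-out: c = 18. Alpha = 726206 / 33554432 = 0.0216; power 0.891. A cut-off of 17 would give alpha 0.054.

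For the other evaluable numbers between 18 and 25:

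| n | c | Alpha | Power |
|---|---|---|---|
| 19 | 14 | 0.032 | 0.837 |
| 21 | 15 | 0.039 | 0.892 |
| 22 | 16 | 0.026 | 0.867 |
| 23 | 16 | 0.047 | 0.929 |
| 24 | 17 | 0.032 | 0.911 |

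Power therefore stays above 0.80 throughout this range.

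**6. What is primary?** Protocol tissue collection gives as the primary objective to compare profiles across three time points and "identify differentially expressed or silenced genes (as determined by ≥ 2 fold change". Statistical Considerations makes the 3-month distance endpoint primary and places the 2-fold gene list among the exploratory analyses.

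**The case against.** The strongest reply is that the arm wording is left over from a design with several treatments, and that the trial can still be analysed. The success endpoint is defined for each woman, the exact test on that endpoint can fail, and a gene-level analysis with false discovery rate control is also planned. All of this stands. It limits the point to the labelled primary rule and its 85%. It does not remove the point, because the primary declaration does not depend on those other analyses.

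A reader might infer more than the protocol supports:

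- **That hCG is bound to be declared the preventive choice, with a 100% false-positive rate.** This holds only if the rule is applied by default to the sole arm. Strictly, the rule is undefined and has no error rate, and a selection rule tests no null hypothesis.
- **That the trial yields no evidence for or against hCG.** The secondary test is error-controlled and uses the same endpoint.
- **That exactly two arms were meant, or that the 85% corresponds to one particular gap.** The text never says two, and the sentence with the 85% names no arms. As shown above, several pairs of rates reach that level.

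Nor can this be left to a statistical analysis plan. The protocol states the rule outright, and a plan that replaced it would contradict the protocol's primary analysis.

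**Conclusion.** The point stands and should be corrected before the analysis. The stated primary rule does not fit the single-arm design and carries no null value, threshold or alpha. Its 85% cannot be reproduced, and it rests on 25 complete pairs where the plan's own drop-out rate leaves 20.

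The remedy is already in the protocol. The exact test keeps its one-sided alpha below 0.05 and has power 0.804 at the expected 20 evaluable women. These figures take as given the plan's null of 0.5, its alternative of 0.80 and its 20% drop-out. The selection probabilities rest on success rates assumed for illustration.

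The conflict over the primary objective is real but separate. The protocol does not settle which version the sponsor intended.

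**What to change.** 1. Delete the sentence that selects between arms and the statement of 85% probability.
2. Make the exact one-sided one-sample test (null 0.5, alpha 0.05) the primary analysis of the 3-month success endpoint. State the critical value for each evaluable number: at least 13/18, 14/19, 15/20, 15/21, 16/22, 16/23, 17/24 or 18/25.
3. Report the success proportion with an exact confidence interval.
4. Remove the multi-arm wording: per arm in Statistical Considerations, each in Special Correlative study #4, and the control group in the exploratory paragraph.
5. Separately, reconcile the primary objective in Protocol tissue collection with Statistical Considerations. If the sponsor confirms the 3-month distance endpoint as primary, label the 2-fold gene list exploratory in both places.

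Cost: an amendment to the primary analysis text. This is a substantive amendment, since it changes the primary analysis, but it needs no extra patients, biopsies or data.

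### The 85% for the primary analysis is tied to 25 complete pairs, but 25 enrolled with 20% drop-out gives about 20, so the figure is unsupported at the expected sample

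*Protocol*

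**What the plan says.** All the sizing statements stand in the protocol's Statistical Considerations section.

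- **Success.** A woman counts as a success if her 3-month expression profile lies closer to the prototypic profile than her baseline profile does: "we will declare woman i a “success".
- **Primary decision rule.** "Whichever arm has a higher proportion of successes is declared the “preventive choice".
- **Primary operating characteristic.** "With complete pre-treatment and post-treatment expression microarray data on 25 women we will correctly identify the changes". The probability claimed for this is 85% or more. No success rate, between-arm difference or tie rule is given with it.
- **Enrolment.** The next sentence: "Assuming a drop-out rate of 20%, we would need to enroll a total of 25 participants per arm".
- **Secondary test.** An exact one-sided, one-sample test at alpha 0.05, with null success probability 0.5 and alternative 0.80: "With data from 18 women we will have at least 80% power".

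The opening summary confirms that 25 is the planned enrolment, all on one treatment: "In this proof-of-concept study, 25 patients will be selected for a 12 weeks treatment of Ovidrel". Special Correlative study #4 likewise refers to 25 women on hCG. The section Criteria for Removal from Study allows replacement of women removed for reasons other than toxicity, but does not require it.

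**The concern.** Two consecutive sentences use 25 for two different quantities: the women with complete paired data on whom the 85% rests, and the women to be enrolled before a 20% loss. With any real drop-out these cannot be equal, so the drop-out allowance has had no effect on the number it should have changed.

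This is the only justification of size given for the primary efficacy analysis. A reader who relies on it would believe that the 85% applies to the trial as enrolled, when it is stated for a sample that the trial does not expect to have. Participants undergo 12 weeks of injections and three biopsy sessions, so the rationale for their number should add up.

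**Working it through.** **Inputs (Statistical Considerations).** Complete pairs for the 85%: 25. Drop-out d = 0.20. Enrolment: 25. Secondary test: null 0.5, alternative 0.80, one-sided alpha 0.05, n = 18.

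**Step 1: the enrolment figure.** Required enrolment = n/(1 − d), rounded up.

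- 25 complete: 25/0.80 = 31.25, so 32. The stated 25 is 7 short.
- The cruder n(1 + d): 25 × 1.20 = 30, which does not give 25 either.
- Starting from 25 enrolled: 25 × 0.80 = 20 expected complete pairs.
- Chance that all 25 complete, if losses are independent: 0.80^25 = 0.004.
- In reverse: 20/0.80 = 25 exactly. The two sentences agree if the completer number is 20.

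**Step 2: can the 85% be reproduced?** Not from the protocol, because no success rates are stated. The rates below are assumptions, used to show the range.

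(a) Read as a choice between two arms with n women each, success rates p₀ and p₁, ties split evenly:

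P(correct choice) = P(X₁ > X₀) + ½ P(X₁ = X₀), with X₀ ~ Bin(n, p₀) and X₁ ~ Bin(n, p₁).

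| Assumed rates | 25 per arm | 20 per arm |
|---|---|---|
| 0.50 vs 0.60 | 0.761 | 0.737 |
| 0.50 vs 0.65 | 0.859 | 0.831 |
| 0.65 vs 0.80 | 0.883 | 0.856 |
| 0.50 vs 0.70 | 0.927 | 0.903 |

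(b) Read as a single-arm majority, i.e. P(X > n/2) with X ~ Bin(n, p):

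| Assumed p | n = 25 | n = 20 |
|---|---|---|
| 0.60 | 0.846 | 0.755 (0.814 with ties split) |
| 0.65 | 0.940 | 0.878 (0.913 with ties split) |

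Depending on the assumption, 20 completers fall below 85% or exceed it. So can 25.

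**Step 3: the secondary test.** The critical value r is the smallest with P(X ≥ r | n, 0.5) ≤ 0.05; power is P(X ≥ r | n, 0.80).

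| Evaluable n | Reject at | Exact alpha | Power at 0.80 |
|---|---|---|---|
| 18 | 13 or more | 0.048 | 0.867 |
| 19 | 14 or more | 0.032 | 0.837 |
| 20 | 15 or more | 0.021 | 0.804 |
| 21 | 15 or more | 0.039 | 0.891 |
| 22 | 16 or more | 0.026 | 0.867 |
| 23 | 16 or more | 0.047 | 0.928 |
| 24 | 17 or more | 0.032 | 0.911 |
| 25 | 18 or more | 0.022 | 0.891 |

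The claim for 18 women is reproduced. Power stays at or above 0.804 for every n from 18 to 25; it is uneven because the test is discrete. Eighteen evaluable women need 18/0.80 = 22.5, so 23 enrolled, which 25 covers. With 25 enrolled and independent 20% losses, the chance of at least 18 completers is 0.891.

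**The case against.** **It is probably a drafting slip.** Since 20/0.80 = 25 exactly, the completer number may have been meant as 20, in which case the enrolment is right. This is plausible, but it is an inference. If it is so, the text is still wrong, and nothing shows whether the 85% was calculated for 20 or for 25.

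**Losses can be replaced.** Criteria for Removal from Study permits this, and it could bring the number of completers above 20. But it is optional, excludes removals for toxicity, and is not invoked in the sample-size paragraph. If replacement were meant to hold completers at 25, the 20% allowance would serve no purpose. It softens the expected 20 without reconciling the two sentences.

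**A reader might infer that the trial misses its 85%.** The protocol does not support that. Without stated success rates the figure cannot be checked at 25 or at 20, and some reasonable rates keep it above 85% at 20.

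**A reader might also count 18 as a third conflicting sample size.** It is not one. It is a sufficient number for a separate, secondary test, and it fits an enrolment of 25 with 20% loss. Nor should the exact-test powers be used to judge the 85%, which belongs to the selection rule.

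**Conclusion.** The contradiction holds, within narrow limits. As written, the number of complete pairs behind the 85% equals the enrolment before a 20% loss. The expected number of pairs is about 20 rather than 25, on the protocol's own drop-out rate and without counting optional replacement. The 85% is therefore unsupported at the expected sample. It also lacks a defined basis: no success rates are stated, and a rule that picks the better arm has nothing to choose between when only hCG treatment is described.

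It does not follow that the trial is under-enrolled and must recruit 32. That would be so only if 25 complete pairs were truly required, and without the basis of the 85% the protocol does not establish it. The secondary claim stands, although at the expected 20 evaluable women the margin over 80% is thin (80.4%).

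This should be fixed: a stated figure is wrong as written, but enrolment, the secondary test and its power claim are unaffected.

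**What to change.** Keep enrolment at 25 and rewrite the sample-size paragraph as follows.

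1. State that 25 women will be enrolled and that, with 20% drop-out, about 20 are expected to have paired arrays.
2. Either restate the 85% for 20 women, giving the success rate or rates and the tie rule it assumes, or withdraw it together with the words *per arm* and the between-arm selection wording.
3. For the secondary exact one-sided test, and labelled as such, give the figures at the expected size: 20 evaluable, reject at 15 or more successes, exact alpha 0.021, power 80.4% at a true success probability of 0.80. Add the figures for 18 evaluable: 13 or more, alpha 0.048, power 86.7%. These describe the secondary test and should not stand in for the primary analysis's 85%.

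The cost is one corrected paragraph and no additional participants. The sponsor must recover the assumption behind the 85%. If it cannot, the figure goes, and the primary analysis is then left without a stated operating characteristic, which the text should say openly.
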